7.9 Safety Assessments

No imputation will be made in case of missing values.

7.9.1 Adverse Events

All AEs for each subject, including multiple occurrences of the same event, will be presented in full in a comprehensive listing including subject number, treatment, severity, seriousness, action taken, outcome, relationship to treatment, onset/stop date and duration. Deaths that occur during the study will be listed.

Duration of the AE and time to the AE occurrence from start of the IMP will be calculated and presented in days (duration = AE stop date – AE start date + 1).

AEs which start on or after dosing that are expressed or exacerbated are defined as treatment emergent adverse events (TEAEs).

The frequency and incidence of TEAEs will be summarized by System Organ Class (SOC) and Preferred Term (PT). The summary will be sorted by International Agreed Order (IAO) for SOC and alphabetical order for PT (or by frequency from the highest to the lowest).

Following summaries of TEAEs will be presented:

- Summary of AEs by SOC and PT
- Summary of AEs by SOC, PT and severity of event
- Summary of AEs by SOC, PT and relationship to treatment

For summaries of AEs multiple occurrences of the same event within a subject will be counted once in the summaries by SOC and PT; multiple occurrences of the same event within a subject will be counted once in the maximum intensity category (severe > moderate > mild) and/or maximum drug relationship category (reasonable possibility > no reasonable possibility). If intensity or relationship is found to be missing the most severe occurrence will be imputed for that particular summary.

Proportion of subjects with any TEAE, subjects with any related TEAE, subjects with any treatment emergent SAE, and subjects with any TEAE leading to discontinuation of the study will be summarized.

7.9.2 Laboratory Tests

All laboratory parameter will be listed.

Laboratory parameter values and changes from baseline, except for urinalysis will be summarized descriptively by analysis visit window.

Clinical significance of laboratory findings will be evaluated by the Investigator with respect to pre-defined clinically relevant ranges taking into account the Investigator site's normal ranges. The laboratory data will be listed in full with clinically relevant values flagged (L=Lower than normal range, H=Higher than normal range or A=Abnormal if no reference range). A listing of laboratory values will be provided for subjects with any clinical significant findings (list relevant laboratory parameters only).

Lab parameter values and changes from baseline will be summarized descriptively by each group (Groups 1, 2 and 3) and analysis visit window.

Shift tables will present the changes in clinically relevant categories from baseline to each scheduled post-baseline visit. The categories will be qualitative values for Urinalysis.

7.9.3 Vital Signs

All vital sign data will be listed.

Vital signs (weight, systolic blood pressure, diastolic blood pressure, pulse rate, body temperature) values and changes from baseline will be summarized descriptively by analysis visit window.

7.9.4 12-lead ECG

All 12-lead ECG (heart rate, RR, PR, QRS, QT, QTcF, overall evaluation) parameters and findings will be listed.

12-lead ECG parameter values and changes from baseline will be summarized descriptively by analysis visit window.

7.9.5 Physical Examinations

All physical examinations data will be listed.

7.9.6 Withdrawals

All subjects who are withdrawn from the study will be listed, and its discontinuation assessment will be excluded from summarized.

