4.5 Withdrawal of individual subjects

A subject will be withdrawn if ANY of the following criteria are met:

- The subject wishes to withdraw from further participation
- The subject is significantly noncompliant with the Protocol
- The subjects is discontinued due to safety reason; continuing in the study would be detrimental to the subject's safety in the opinion of the Investigator, such as
 - The subject experiences intolerable AEs or SAEs
 - The subject has clinically significant changes in safety parameters at any of the post-dose time points, as confirmed with a repeat assessment performed as soon as possible after the initial out-of-range result

In addition, a subject may be withdrawn at any time for any reason other than those listed here.

If a subject is discontinued prematurely from the study, the date the subject is withdrawn from the study and the reason for withdrawal will be recorded on the CRF.

In case of withdrawal of a subject, the Follow-up Visit assessments should be performed, as far as possible (Section 5.2.3).

Any withdrawal due to an AE or for any safety reason should always be considered serious.

Any unresolved AE or SAE will be followed up according to Section 8.9.

In the event that a subject elects not to return to the study center for the end of study visit, the Investigator must make every effort to contact the subject to review all AEs. In the event that a subject drops out of the study at any time, the reason for discontinuation must be fully documented in the source documents and the CRF. The study center personnel will document the AEs and any other assessments in the source documents and will make every effort to complete all required end of study assessments.

Subjects withdrawn for non-treatment-related reasons may be replaced at the discretion of the Sponsor and Investigator. Replacement subjects will receive the treatments intended for the withdrawn subject.

Criteria for amendment of dose in subjects with mild renal impairment (Group 1)

The subjects with mild renal impairment will be treated first. The second subject with mild renal impairment will not be treated until the completion of review for safety and PK profile in the first treated subject by the Sponsor and the Investigator. [REDACTED]

[REDACTED]

Procedure and criteria for starting treatment of subjects with moderate renal impairment (Group 2)

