5.2.3 Follow-up period (Day 7 /+2 days)

Subjects will return to the study center on Day 7 for a Follow-up Visit. The following assessments will be performed (refer to the Time and events schedule [Table 5] for further details):

- Physical examination (including body weight)
- 12-lead ECG
- Vital signs (including supine blood pressure, pulse rate and infra-axillary body temperature)
- Routine laboratory evaluations (haematology; biochemistry; coagulation; urinalysis; pregnancy test for female)
- eGFR and eCLcr
- AE and concomitant medication recording

Subjects who are withdrawn from the study should, where possible, complete the procedures scheduled for the Follow-up Visit as soon as possible after withdrawal.

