5.2 Analysis Time Window for Visits

Analysis time windows for blood sampling for PK measurements are as follows.

Analysis time windows for safety evaluation are as follows.

Screening (Day -21 to Day -2)	Not specified
Hospitalization (Day -1)	Not specified
Before dosing (Day 1)	Before dosing time
24 h and 48 h after dosing (Day 2 and Day 3)	Scheduled time \pm 1 hour (except for urinalysis) Until scheduled time + 1 hour (urinalysis)
Follow-up (Day 7 + 2days)	Not specified

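### SAP 7.9.6 leaves discontinuation values out of the summaries of measured safety data even when they fall inside a scheduled window

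*SAP*

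**What the plan says.** - SAP 7.9.6, within the Safety Assessments section: "All subjects who are withdrawn from the study will be listed, and its discontinuation assessment will be excluded from summarized". It names no table and sets no time window.
- Protocol 4.5: "In case of withdrawal of a subject, the Follow-up Visit assessments should be performed, as far as possible". Protocol 5.2.3 asks withdrawn subjects to "complete the procedures scheduled for the Follow-up Visit as soon as possible after withdrawal".
- Protocol 4.5 lists a clinically significant post-dose change in safety parameters, confirmed by a repeat assessment, among the reasons to withdraw a subject. It adds: "Any withdrawal due to an AE or for any safety reason should always be considered serious".
- Protocol 10.2 puts every dosed subject in the safety analysis set.
- SAP 5.2 sets the safety windows: scheduled time ± 1 hour at 24 h and 48 h (for urinalysis, up to scheduled time + 1 hour). Follow-up is labelled Day 7 + 2 days, with its analysis window marked as not specified.
- SAP 7.9.2 to 7.9.4 summarise laboratory, vital-sign and ECG values by visit window; for ECG: "12-lead ECG parameter values and changes from baseline will be summarized descriptively by analysis visit window". For laboratory categories: "Shift tables will present the changes in clinically relevant categories from baseline to each scheduled post-baseline visit". SAP 7.9.2 also promises a listing: "A listing of laboratory values will be provided for subjects with any clinical significant findings".
- SAP Section 9, on data not summarised or presented, is marked not applicable.

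**The concern.** The exclusion depends on why an assessment was made, not on when. A value obtained at discontinuation is left out of the group summary even if its timing would place it in the 24 h, 48 h or Follow-up row.

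This is not neutral. Abnormal safety parameters can cause the withdrawal, so the excluded values may come from the subjects whose measurements moved most. Protocol 8.5 calls change from baseline an important indication in renal impairment, and Protocol 1.4 names BUN, creatinine, AST and ALT among the parameters to monitor. In groups of 8 or 11, one subject can set the group maximum.

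At stake is whether the group tables of measured values can show a peak first seen at discontinuation. No PK endpoint is involved.

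**Working it through.** The plan gives no figure to reproduce here. The sample size is not power-based, and no withdrawal rate is stated. The check is a comparison of sections plus a small illustration.

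**1. Which outputs the rule reaches (SAP 12.2)**

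| Output | Affected by 7.9.6? |
|---|---|
| Laboratory summaries and clinical-assessment table | Yes |
| Weight, vital signs, ECG, and the vital-sign and ECG overall evaluations | Yes |
| Urinalysis shift table | Already limited to scheduled visits by 7.9.2; 7.9.6 adds only the in-window case |
| TEAE tables, including SAEs and TEAEs leading to discontinuation (7.9.1) | No |
| Listings (12.1; 7.9.2 to 7.9.4) | No |

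SAP 12.2 contains no worst-value or early-withdrawal table that would pick up an excluded value.

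**2. What happens to a discontinuation value, by timing**

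| Timing | As written | If 7.9.6 were simply deleted |
|---|---|---|
| Within 24 h or 48 h ± 1 hour | In no row | In that visit's row |
| Day 7 to Day 9 | In no row, if classed as a discontinuation assessment | In the Follow-up row |
| Outside every window | In no row | In no by-visit row |

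The exclusion itself therefore bites in the first two lines. In the third, the by-window design already keeps the value out.

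**3. Illustration with assumed values**

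Inputs: group sizes 8 (Group 2) and 11 (Groups 1 and 3) from Protocol 3.1. Assume one subject has creatinine +50% at the discontinuation assessment and all others are unchanged.

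In-window case, mean change in that visit's row:
- As written, the subject is absent: 0/7 = 0% for Group 2, and 0/10 = 0% for a group of 11. Maximum 0%.
- Value included: 50/8 = 6.25%, or 50/11 = 4.5%. Maximum +50%.

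Out-of-window case, assuming the same subject was at +10% at 24 h and 48 h:
- The 24 h and 48 h means are 10/8 = 1.25% or 10/11 = 0.9%, with or without 7.9.6.
- The highest change in any group summary is +10% as written, and still +10% if 7.9.6 is only deleted. It becomes +50% only if a summary is added that accepts off-schedule values.

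**4. How often this could arise (assumed withdrawal rates)**

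The chance of at least one post-dose withdrawal is 1 − (1 − p)^n.

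| Assumed p | All 30 subjects | Group 2 (n = 8) |
|---|---|---|
| 1% | 26% | 8% |
| 2% | 45% | 15% |
| 5% | 79% | 34% |
| 10% | 96% | 57% |

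These are chances of any withdrawal. The chance of one with a notable value at that assessment is lower.

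**The case against.** The strongest reply is that off-schedule values do not belong in by-visit means, and that safety is covered by other routes. Much of this stands.

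- Protocol 10.3.5.4 and 10.3.5.5 plan summaries at each time point, and Protocol 10.3.2 leaves data handling to the SAP. The rule is therefore permitted. A reader might infer a breach of Protocol 10.3.5.2, which says all safety variables will be summarised, but the documents do not support that.
- A reader might infer that every safety summary is affected. It is not. Clinically significant abnormalities are AEs (Protocol 6.7.2 to 6.7.4), withdrawals for a safety reason count as serious, and SAP 7.9.1 summarises treatment-emergent SAEs and TEAEs leading to discontinuation. The assumed +50% creatinine could well be judged clinically significant and reach those tables.
- A scheduled 24 h or 48 h value that led to withdrawal stays in its row. Only the discontinuation assessment is lost.
- A reader might take the gap between 30 enrolled and 24 completing as the number of subjects the rule removes from the Follow-up row. That gap is headroom, not a forecast, and withdrawn subjects may be replaced. A subject whose only late assessment is off schedule would be missing from that row with or without 7.9.6.
- Someone who has the Follow-up procedures on Day 7 to 9 may simply be counted as having attended the visit. The documents do not say how this is classified, so the Day 7 case is less certain than the 24 h and 48 h cases.

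The reply does not justify dropping a value that falls inside a scheduled window. AE tables count events and do not show the size of a change. A value not judged clinically significant reaches listings only.

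**Conclusion.** The point holds as a minor one. As written, SAP 7.9.6 discards measured safety values taken at discontinuation even when they fall inside a scheduled window, and no planned group maximum or change-from-baseline summary can show a peak first seen there. For off-schedule values, the gap comes mainly from the by-window design; 7.9.6 only confirms it.

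The effect is nil without withdrawals. Otherwise it is small, since this is a single-dose study with confinement to Day 3, and full listings and the AE and SAE routes remain. In the assumed in-window example, one subject's exclusion moves a row's mean change by 6.25 percentage points (n = 8) or 4.5 (n = 11), and its maximum from +50% to 0%.

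The conclusion assumes that 7.9.6 is applied literally. The part of the SAP between Sections 3 and 5 was not available for this review, so the absence of a reason or timing limit is confirmed only for the remaining text.

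**What to change.** Replace the exclusion in SAP 7.9.6 with:

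> A discontinuation assessment that falls within any scheduled analysis window (24 h or 48 h ± 1 hour, or Day 7 to Day 9) is included in that visit's row. One outside every window is not included in by-visit rows but is included in a per-group maximum post-dose change from baseline for creatinine, BUN, AST and ALT, and is shown in a separate early-withdrawal row with the post-dose day.

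Three details complete the change:
- Say which value the row uses if a scheduled and a discontinuation assessment fall in the same window.
- Leave the urinalysis shift table on scheduled visits.
- Cross-refer from SAP Section 9 for values kept out of the by-visit rows.

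The cost is one replaced sentence and one or two extra descriptive rows, with no new data. The downside is that the early-withdrawal row will hold few subjects at mixed post-dose days, so it cannot support comparison between groups. It can be omitted if nobody withdraws.

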7.9.7 Other Safety Assessments

Not applicable in the study.

8. CHANGES FROM THE PROTOCOL

Not applicable in the study.

9. DATA NOT SUMMARISED OR PRESENTED

Not applicable in the study.

11. VALIDATIONS

SAS® for Windows (release 9.3 or a later version) will be used for statistical analyses.

[REDACTED] will be used to calculate Pharmacokinetics Parameters.

The quality of statistical results will be ensured by double programming at ICRO.

12. LISTINGS, TABLES AND FIGURES

12.1 Listings

No.	Title of listing	Analysis Population/Dataset
16.2.1 – Subject Disposition		
	Subject Dispositions	All Subjects
	Withdrawals	All Subjects
16.2.2 – Inclusion and Exclusion Criteria		
	Inclusion and Exclusion Criteria	All Subjects
16.2.3 – Demography and Baseline Characteristics		
	Demography and Baseline Characteristics	All Subjects
16.2.4 – Medical History and medications		
	Medical history and Complications	All Subjects
	Prior and Concomitant Medications	All Subjects
16.2.5 – Exposure and Compliance		
	Study Drug Exposure and Compliance	All Subjects
16.2.6 – Pharmacokinetics		
	List of Blood Collection Time for Pharmacokinetic Evaluation	All Subjects
	List of Plasma Concentrations	All Subjects
	List of Plasma Pharmacokinetic Parameters	All Subjects
16.2.7 – Adverse Events		
	Adverse Events	All Subjects
16.2.8 – Laboratory Parameters		
	Laboratory Tests - Haematology	All Subjects
	Laboratory Tests - Biochemistry	All Subjects
	Laboratory Tests - Coagulation	All Subjects
	Laboratory Tests - Urinalysis	All Subjects
16.2.9 – Other safety assessments		
	Physical Examinations, Weight and BMI	All Subjects
	Vital Signs	All Subjects
	12-Lead ECG	All Subjects

12.2 Tables

No.	Title of table	Analysis Population/Dataset
14.1 – Study		
	Subjects Dispositions and Analysis Population	All Subjects
	Demography and Baseline Characteristics	Safety, PK
	Summary of Prior Medications	Safety
	Summary of Concomitant Medications	Safety
14.2 – Pharmacokinetics		
	Descriptive Statistics for Plasma Concentrations	PK
	Descriptive Statistics for Plasma Pharmacokinetic Parameters	PK
	Estimate of the Ratio of Geometric LSmeans for pharmacokinetic parameters of each renal impairment group (Groups 1 and 2) with relative to the normal renal function group (Group 3)	PK
14.3 – Safety		
	Summary of Treatment Emergent Adverse Events	Safety
	Incidence and Frequency of Treatment Emergent Adverse Events by System Organ Class and Preferred Term	Safety
	Incidence and Frequency of Treatment Emergent Adverse Events by System Organ Class, Preferred Term and Severity	Safety
	Incidence and Frequency of Treatment Emergent Adverse Events by System Organ Class, Preferred Term and Relation to Study Drug	Safety
	Summary of Laboratory Tests - Haematology	Safety
	Summary of Laboratory Tests - Biochemistry	Safety
	Summary of Laboratory Tests - Coagulation	Safety
	Summary of Laboratory Tests - Urinalysis	Safety
	Summary of Laboratory Tests – Clinical Assessment	Safety
	Shift table of Laboratory Tests - Urinalysis	Safety
	Weight	Safety
	Vital Signs	Safety
	Vital Signs - overall evaluation	Safety
	12-Lead ECG	Safety
	12-Lead ECG - overall evaluation	Safety

12.3 Figures

No.	Title of figure	Analysis Population/Dataset
14.2 – Pharmacokinetics		
	Profile of Mean Plasma Concentrations	PK
	Scatter plots of the PK parameters of (AUC _{0-last} , AUC _{0-∞} , [REDACTED] and C _{max} of MCI-186 and the sulfate conjugate) vs (eGFR and eCLcr) plot for all subjects overlaid in one graph	PK

No.	Title of figure	Analysis Population/Dataset
16.2.6 – Pharmacokinetics		
	Profile of Individual Plasma Concentrations	PK

13. REVISION HISTORY FOR SAP AMENDMENTS

Version 2.0 (20 June, 2018)

It reflects the results of the data review meeting on 29 May, 2018.

In list of abbreviations and Section 5.3, Pearson's r deleted and Spearman's ρ added.

In Section 1, as protocol changes, the applicable protocol version number has been changed.

In Section 7.8.2, the axis type of the scatterplot has been changed from logarithmic axis to linear axis.

In Section 12.1, "All Subjects" were specified in all parts of the "Analysis Population/Dataset" column.

APPENDIX 1 – PHARMACOKINETIC PARAMETER CALCULATIONS

- Actual blood sampling times for the assay of MCI-186 will be used in the calculation of pharmacokinetic parameters
- All concentrations below the LLOQ will be set at zero for pharmacokinetic calculations
- When [REDACTED] is missing (or cannot be determined), [REDACTED] points will not be calculated

PK Parameter Calculations		
Parameters	Unit	Calculation
AUC _{0-last}	h·ng/mL	will be calculated using the linear trapezoidal method and actual times $AUC_{0-\text{last}} = \sum_{i=1}^n \frac{t_i - t_{i-1}}{2} (C_{i-1} + C_i)$
AUC _{0-∞}	h·ng/mL	$AUC_{0-\infty} = AUC_{0-\text{last}} + \frac{C_{\text{last}}}{\lambda_z}$
C _{max}	ng/mL	will be determined using maximum drug concentration

PK Parameter Calculations		
Parameters	Unit	Calculation
$t_{1/2}$	h	$t_{1/2}$ will be determined as: $t_{1/2} = \frac{\log_e(2)}{\lambda_z}$
